654 The first training session will consist of generic training on resuscitation and the study procedures, data collection and
655 we will explain the trial, equipoise and the need to follow protocol. We will then invite paramedics to sign a consent
656 form or leave training, without prejudice. We will randomise paramedics who have consented to take part in the trial to
657 one of the two groups (i-gel or intubation). The paramedics will then be divided into two groups according to their
658 allocation, and complete technical training specific to each trial group. We will then answer any questions that have
659 arisen and complete the training session.

660

661 **5.3.2 Tracheal Intubation**

662

663 Tracheal intubation requires the use of a laryngoscope to see the patient’s larynx, followed by the placement of a tube
664 at the correct level in the trachea, and is usually undertaken only by doctors and paramedics. The ease with which
665 tracheal intubation can be accomplished varies from patient to patient, and it requires training to develop this skill,
666 followed by ongoing practice to ensure that the skill is maintained. Sometimes tracheal intubation cannot be achieved,
667 or the tracheal tube may be placed in the patient’s oesophagus by mistake. If the latter circumstance goes unrecognised
668 the patient is unlikely to receive any oxygen during their cardiac arrest and it is well recognised that, even if a tracheal
669 tube is correctly placed, the technical demands of achieving intubation can lead to long pauses in the chest
670 compressions that are vital to resuscitation success [18]. To ensure that the standard care pathway is optimised, and the
671 chance of successful tracheal intubation maximised, all participating paramedics will be equipped with an intubating
672 bougie and end-tidal carbon dioxide monitoring.

673

674 **5.3.3 Placement of i-gel**

675

676 Placement of an i-gel is much simpler than tracheal intubation, and does not require the use of a laryngoscope. The i-
677 gel device is simply inserted, in the correct orientation, into the patient’s mouth and pharynx, where it usually provides
678 a direct channel from the mouth to the opening of the trachea. Sometimes however the i-gel will not form a satisfactory

679 seal, leading to leakage and a failure to ventilate the lungs. There is also a risk that gastric contents (vomit) will

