1643 with **Appendix A**.

1644

1645 **2. STUDY BACKGROUND AND OBJECTIVES**

1646 **2.1 Study background**

1647 AIRWAYS-2 is a randomised controlled trial (RCT) in four UK ambulance trusts (South Western Ambulance
1648 Service NHS Foundation Trust (SWAST), East of England Ambulance Service NHS Trust (EAST), East
1649 Midlands Ambulance Service NHS Trust (EMAS) and Yorkshire Ambulance Service NHS Trust (YAS)) with
1650 cluster randomisation at the paramedic level.

1651 Two advanced airway management devices for the treatment of out of hospital cardiac arrests (OHCA) are
1652 compared: the i-gel, a second generation supraglottic airway device (SGA), and tracheal intubation, currently
1653 standard practice.

1654 Ambulance staff performing the airway management are unable to be blinded to allocation but the patients
1655 and research staff assessing all outcomes post hospital admission (including the primary outcome) will be
1656 blinded.

1657 **2.2 Study objectives**

1658 1. To estimate the difference in the primary outcome of mRS at hospital discharge or 30 days post OHCA,
1659 whichever comes first, between groups of patients managed by paramedics randomised to use either the i-gel
1660 or intubation as their initial advanced airway management strategy following OHCA.

1661 2. To estimate differences in secondary outcome measures relating to airway management, hospital stay and
1662 recovery at 3 and 6 months between groups of patients managed by paramedics randomised to use either the i-
1663 gel or intubation.

1664 3. To estimate the comparative cost effectiveness of the i-gel and intubation, including estimating major in
1665 hospital resources and subsequent costs (length of stay, days of intensive and high dependency care, etc.) in
1666 each group. This objective will not be covered in this analysis.

1669 **2.3 Primary outcome**

1670 The primary outcome is mRS assessed at hospital discharge (or 30 days post OHCA if patient remains in
1671 hospital until this time). The mRS incorporates survival status and will be analysed as good recovery (scores 0
1672 to 3) compared to poor recovery/death (scores 4 to 6).

1673 **2.4 Secondary outcomes**

1674 The protocol includes the secondary outcomes listed below (a health economic outcome is also listed in the
1675 protocol but excluded here).

1676 All enrolled patients:

- 1677 1. Initial ventilation success, defined as visible chest rise and end tidal carbon dioxide (ETCO₂) at the first

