Protocol deviation 5	if (paramedic allocated to i-gel and number of i-gel attempts made before switching to intubation or other SGA = 1 or (paramedic allocated to intubation and number of intubation attempts made before switching to i-gel or other SGA = 1), then = Yes if (paramedic allocated to i-gel and number of i-gel attempts made before switching to intubation or other SGA ≠ 1 and at least one advanced airways management attempt recorded) or (paramedic allocated to intubation and number of intubation attempts made before switching to i-gel or other SGA ≠ 1 and at least one advanced airways management attempt recorded), then = No Else missing
POPULATION 2:	
Initial ventilation success in first or second attempt	If i-gel is used before intubation or other SGA: If ventilation success = yes on first i-gel attempt, then = Yes If ventilation success = no on the first i-gel attempt and the next advanced attempt is also i-gel and on that attempt ventilation success = yes, then = Yes If ventilation success = no on first i-gel attempt and the next advanced attempt is also i-gel and ventilation success = no, then = No If ventilation success = no on first i-gel attempt and (there is no further attempt or the next advanced attempt is intubation or other SGA), then = No If intubation is used before i-gel or other SGA: If ventilation success = yes on first intubation attempt, then = Yes If ventilation success = no on the first intubation attempt and the next advanced attempt is also intubation and on that attempt ventilation success = yes, then = Yes If ventilation success = no on first intubation attempt and the next advanced attempt is also intubation and ventilation success = no, then = No If ventilation success = no on first intubation attempt and (there is no further attempt or the next advanced attempt is i-gel or other SGA), then = No If other SGA is used before i-gel or intubation:

New variable	Rules

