1940 the best fit in terms of information criteria such as AIC, BIC and likelihood ratio tests will be used.

1941 **6.2.3 Statistical significance**

- 1942 For hypothesis tests two-tailed p-values < 0.05 are considered statistically significant.
- 1943 **6.2.4 Model assumptions**
- 1944 For all methods outlined underlying assumptions will be checked using standard methods, e.g. residual plots,
1945 tests for proportional hazards, etc. If assumptions are not valid then alternative methods of analysis will be
1946 sought. If outlying observations are found which mean models do not fit the data adequately, such
1947 observations will be excluded from the main analyses and comments made in footnotes.
- 1948 **6.2.5 Subgroup analyses**
- 1949 Two subgroup analyses for the primary outcome are specified in the protocol: Utstein comparator group vs
1950 non-comparator group and arrest witnessed by ambulance staff or not (**Figure F7**).
- 1951
- 1952 Due to concerns regarding ventilation success raised during the trial, a subgroup analysis of the primary
1953 outcome comparing patients whose i-gel or intubation airway management attempt(s) were or were not
1954 ‘successful’ during the first and/or second attempt (see section 5.2 for definition) will also be performed. This
1955 analysis will be performed per-protocol and as such will only include patients who received at least one
1956 advanced airway management attempt using an i-gel and/or intubation tube.
- 1957
- 1958 Subgroup effects will be fitted by adding a “sub-group x intervention” interaction term to the analysis model.
- 1959 **6.2.6 Sensitivity analyses**
- 1960 For the primary outcome, the following sensitivity analyses will be performed:
- 1961
 - ITT analysis including only patients who received at least one advanced airway management attempt
1962 using an i-gel and/or intubation tube.
 - Per-protocol analysis including only patients who received at least one advanced airway management
1963 attempt using an i-gel and/or intubation tube (see section 6.2.5 for additional sub-group analysis for
1964 this outcome).
 - ITT analysis including all patients who were attended by an AIRWAYS-2 paramedic but not
1965 resuscitated.
- 1966
- 1967
- 1968 **6.2.7 Missing data**
- 1969 In all tables missing data will be indicated by footnotes. If the amount of missing data differs substantially
1970 between treatment groups potential reasons will be explored.
- 1971 Missing predictors:

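### The added subgroup analysis in SAP 6.2.5 splits the primary outcome by ventilation success, which is itself a result of the device, so its interaction test and stratum odds ratios do not support a device comparison

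*Protocol*

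**What the plan says.** SAP 6.2.5 first names the two subgroup analyses taken from protocol 6.2: the Utstein comparator group, and arrest witnessed by ambulance staff. It then adds a third: "Due to concerns regarding ventilation success raised during the trial, a subgroup analysis of the primary" "outcome comparing patients whose i-gel or intubation airway management attempt(s) were or were not" successful at the first and/or second attempt. This third analysis is per-protocol. It is limited to patients with an i-gel or tube attempt and, under SAP 6.2.2, grouped by the first advanced airway used. The section ends: "Subgroup effects will be fitted by adding a “sub-group x intervention” interaction term to the analysis model". No exception is made for the third analysis.

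The splitting variable also appears in three other places in the SAP:

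- Section 2.4 lists it as secondary outcome 1: "Initial ventilation success, defined as visible chest rise and end tidal carbon dioxide (ETCO₂) at the first" or second attempt.
- Section 5.4 derives it from what happened with the device used first. For example, "If ventilation success = no on first intubation attempt and (there is no further attempt or the next advanced attempt is i-gel or other SGA), then" the patient is coded as a failure. (Section 6.2.5 points to 5.2 for this definition, but 5.2 covers compression fraction.)
- Section 6.2.2 and Table T7 treat it as a binary outcome, compared between allocated groups by odds ratio.

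**The concern.** An interaction test asks whether a treatment effect differs between kinds of patient. That needs kinds of patient defined independently of treatment. The two protocol subgroups rest on presenting rhythm and on who witnessed the arrest, both settled before the trial airway is used. Ventilation success is settled afterwards, by the device.

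A patient in whom a tube succeeds and a patient in whom an i-gel succeeds need not be the same sort of patient, and the same holds for failures. The protocol gives some reason to expect a difference. Section 5.3.2 says of ease that "tracheal intubation can be accomplished varies from patient to patient, and it requires training to develop this skill", while 5.3.3 describes i-gel placement as much simpler and names a poor seal as the way it fails. If airway ease is related to prognosis, the device contrast within each stratum compares unlike groups.

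At stake is a misleading secondary result. The analysis exists because of concerns about ventilation success raised during the trial, so readers will look at it. It could show a device effect among failures, or opposite effects in the two strata, when neither device changes recovery.

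**Working it through.** The plan gives no operating figure for this analysis, so there is none to reproduce. The question is how often the nominal 5% test rejects when the device has no effect on recovery.

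**Inputs from the documents.** Good recovery is 9% (protocol 4.7, the centre of 8% and 10%). The two-sided significance level is 5% (SAP 6.2.3). The planned size is 4,535 per group (protocol 4.7).

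**Assumptions not in the documents.** 3,800 patients per device, below 4,535 because only patients with an attempt count; success of 87% (i-gel) and 79% (tube); and all slopes below. Clustering is ignored. At ICC 0.005 and 7 patients per paramedic the design effect is 1 + 6 × 0.005 = 1.03, too small to matter here.

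**Model.** Each patient has an airway-ease score u ~ N(0,1).

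- logit P(success on device d) = c_d + a_d·u
- logit P(good recovery) = c + b·u, with no device term

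The intercepts are set to give the success and recovery rates above. The test statistic is the difference between the log odds ratios (i-gel versus tube) in the success and failure strata, divided by its standard error.

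**Worked case: slopes a = 0.3 (i-gel) and 1.5 (tube), b = 1.0.**

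| Stratum | i-gel recovery (n) | Tube recovery (n) | Odds ratio |
|---|---|---|---|
| Success | 9.27% (3,306) | 10.41% (3,002) | 0.88 |
| Failure | 7.21% (494) | 3.70% (798) | 2.02 |

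- Overall recovery is equal: 0.87 × 9.27 + 0.13 × 7.21 = 9.0% and 0.79 × 10.41 + 0.21 × 3.70 = 9.0%.
- The ratio of odds ratios is 0.434, with log −0.834.
- The variance, summing 1/[n·p(1−p)] over the four cells, is 0.0036 + 0.0036 + 0.0303 + 0.0352 = 0.0726, so the SE is 0.269.
- z = −0.834/0.269 = −3.10, and the rejection probability is Φ(3.10 − 1.96) = 87%.

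**Range of slopes (rejection rate of the 5% interaction test).**

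| Slopes, i-gel vs tube | b = 0.5 | b = 1.0 | b = 1.5 |
|---|---|---|---|
| 1.0 vs 1.0 | 5% | 5% | 5% |
| 0.7 vs 1.0 | 7% | 12% | 16% |
| 0.8 vs 1.2 | 8% | 14% | 21% |
| 0.5 vs 1.0 | 12% | 29% | 45% |
| 0.3 vs 1.5 | 42% | 87% | 98% |

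**Equal slopes do not rescue the stratum odds ratios.** With both slopes 1.0, b = 1.0, and success of 90% versus 75%, the interaction test stays near 5%. The odds ratio among successes is nevertheless 0.91, and its own 5% test rejects about 20% of the time (21% to 23% in simulation).

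**A second model, with patient types and no device effect.** Take 4,535 per arm and 90% versus 80% success. In 80% of patients both devices succeed, in 10% only the i-gel does, and in 10% neither does.

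- Recovery of 10%, 10% and 2% by type gives 9.2% overall in both arms. The odds ratio is 1.00 among successes. Among failures it is (0.02/0.98)/(0.06/0.94) = 0.32. Simulated rejection of the interaction is 93%.
- Recovery of 10%, 5% and 3% gives simulated rejection of 9%.
- If recovery is unrelated to type, rejection is 5%.
- The overall device comparison rejects about 5% of the time in every case.

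**The case against.** The strongest reply is that this is a secondary analysis, openly labelled per-protocol, with its origin disclosed. No decision rule depends on it, and SAP 6.2.8 promises care in interpretation. All of that is true, and it limits the consequence. It does not make the split valid. The per-protocol label concerns who is included and how patients are grouped, and the split would be unsound even with every patient included. The care in 6.2.8 concerns the number of tests and the consistency of estimates; nothing in 6.2.5 calls this split descriptive or warns that it follows device use.

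A second reply is that success depends partly on operator skill, which belongs to a randomised paramedic stratified by experience and need not track patient prognosis. That stands: it would dilute the bias, and the documents do not say by how much.

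Three stronger readings go beyond the text:

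- **The test is badly inflated in this trial.** A reader might infer this from the 42% to 98% row, but that row needs a five-fold slope contrast. The documents give no success rates, no slopes and no link between airway ease and recovery.
- **The result will sit beside the baseline subgroups in Figure F7.** SAP 6.2.5 cites F7 only for the two protocol subgroups, the visible title gives ambulance-witnessed arrest as its example, and the figure is not shown.
- **The SAP states a wrong null hypothesis.** It states none for this analysis, only that an interaction term will be added.

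**Conclusion.** The point holds as one of analysis choice. By the SAP's own definitions, ventilation success is a post-randomisation outcome of the device, and 6.2.5 uses it as an effect modifier of that device in an interaction test. The test and the stratum odds ratios can depart from the null with no device effect on recovery.

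Inflation of the interaction test is not automatic. It requires success to be related to prognosis, and the devices to differ in how often they fail or in which patients. Under the assumptions above, rejection runs from the nominal 5% to 98%, and the documents do not say where in that range the trial lies. The primary intention-to-treat analysis, by allocation of the first trial paramedic on scene, is unaffected. The change should be made, but the trial's main conclusion does not turn on it.

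**What to change.** In SAP 6.2.5, delete the interaction test and any between-device odds ratio or p-value for the ventilation-success split, and remove it from Figure F7 if it is shown there. Restrict the interaction sentence to the Utstein comparator and ambulance-witnessed subgroups.

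If the split is kept, show mRS as counts and percentages by success, arranged by device used first. That matches how 5.4 defines success; arranging by allocated group would mix devices wherever patients crossed over. Label it descriptive, and note that the split follows device use and does not support a device comparison, since even a plain table invites reading across columns. Correct the cross-reference from 5.2 to 5.4.

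Address the concern that prompted the analysis through the comparison of ventilation success by allocated group already planned in Table T7. The cost is SAP wording and one lost p-value; no new data are needed.
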